11.4 Data Analyses

The overall significance level for this study will be 2.5% using one-sided hypothesis tests. Results from Stage 1 will be reported using descriptive statistics and confidence intervals. Primary statistical comparisons of efficacy results will use only data from Stage 2; however, data from Stage 1 patients will be combined with data from patients receiving ACM in Stage 2 for secondary efficacy analyses. Details of the analyses planned for this study are provided in the Statistical Analysis Plan under separate cover.

Stage 2 complete remission (CR) rates will be compared across treatment groups using the Cochran-Mantel-Haenszel general association test stratified by response to most recent induction therapy (refractory [persistent disease or CR duration <90 days], early relapse [CR duration 90 days to 1 calendar year], or late relapse [CR duration >1 calendar year but <24 months]). The same test will be applied to assess statistical significance of secondary response rate endpoints. Control of the overall 2.5% type-1 error rate for multiple comparisons will be achieved using the hierarchical closed test procedure.

Treatment-group distributions of time-to-event endpoints will be compared using the log-rank test stratified by response to most recent induction therapy.

Incidence rates of TEAEs will be summarized within treatment group at the MedDRA preferred term and primary system organ class levels. Similar summaries will be made for subsets of AEs such as (1) those judged by the Investigator to be related to study treatment, and (2) SAEs.

Other routine safety assessments (eg, clinical laboratory parameters and vital signs) will be summarized by treatment group using mean, standard deviation, median, minimum and maximum changes from baseline values.

A DSMB will monitor key outcomes from the study.

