4.1 Overall Study Design

This is a Phase 2, open-label, randomized, multicenter, two-stage study to determine if MCL-1 dependence demonstrated by mitochondrial profiling in bone marrow samples will increase the Complete Remission (CR) rate after ACM treatment.

Stage 1 of the study will be single arm (ACM), conducted similarly to the first stage of a Simon 2-stage design. Patients with relapsed or refractory AML with demonstrated MCL-1 dependence of $\geq 30\%$ by mitochondrial profiling in bone marrow will be screened according to study inclusion and exclusion criteria up to 14 days before the initiation of ACM study treatment. Once ≥ 13 patients enrolled in Stage 1 exhibit a CR, CRi, or CRp, enrollment into Stage 1 will close and additional patients will be enrolled in Stage 2 of the study.

Enrollment into Stage 1 will be limited to no more than 23 evaluable patients, however enrollment into Stage 2 may be initiated at any point after confirming CR, CRi or CRp responses in 13 Stage-1 patients.

In Stage 2, patients with relapsed or refractory AML with demonstrated MCL-1 dependence of $\geq 30\%$ by mitochondrial profiling in bone marrow will be randomized 1:1 to receive either ACM or CM. Patients will be screened for study inclusion and exclusion criteria up to 14 days before the initiation of study treatment.

Response assessments in Stage 1 are defined by the International Working Group Criteria [20] and 2010 European LeukemiaNet (ELN) [21]. The 2017 ELN criteria will be used to determine patient responses during Stage 2. Response assessments ([Appendix E](#)) will include:

- CR rate = Percentage of patients achieving CR
- Combined CR Rate = Percentage of patients achieving:
 - CR = Bone marrow blasts $< 5\%$; absence of blasts with Auer rods; absence of extramedullary disease; hematologic recovery (absolute neutrophil count [ANC] $> 1000 \mu\text{L}$ and platelet count $> 100,000 \mu\text{L}$); independence of red cell transfusions; *plus*
 - CRi = Meets all CR criteria except for residual neutropenia (ANC $< 1000 \mu\text{L}$) or lack of recovery of any other hematopoietic cell; *plus*
 - CRp = Meets all CR criteria except for residual thrombocytopenia (platelet count $< 100,000 \mu\text{L}$)[†]

- Combined Response Rate = Percentage of patients achieving:
 - CR
 - CRi
 - CRp †
 - PR = Meets all hematologic values required for CR but with a decrease of at least 50% in the percentage of blasts to $\geq 5\%$ to $\leq 25\%$ in bone marrow

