11.2 Sample Size

11.2.1 Sample Size in Stage 1

The sample size of 23 eligible patients for Stage 1 was selected because it allows estimation of the remission rate by means of a 90% confidence interval with maximum width of ±17%. Although this study does not follow a Simon 2-stage design, 23 patients is consistent with the sample size for Stage 1 of the Simon 2-stage minimax design with 80% power for testing the null hypothesis that the remission rate is 50% against a one-sided alternative at the 5% level of significance when the actual remission rate is 70%. In the Simon 2-stage design described, the study would continue to Stage 2 only if 13 patients achieve remission out of a maximum of 23 eligible patients. Therefore, this was selected as the requirement to proceed to Stage 2 of this study. However, the study may proceed to Stage 2 as soon as 13 patients achieve remission.

The primary objective of Stage 1 is to determine the CR rate in patients with relapsed or refractory AML with MCL-1 dependence of $\geq 30\%$. Thus a patient who leaves the study prior to providing a bone marrow sample adequate for assessing response to treatment will be replaced by another eligible patient.

11.2.2 Sample Size in Stage 2

The planned sample size of 56 patients (28 per treatment arm) in Stage 2 of this study provides 90% power to reject the null hypothesis of equal CR rates across treatment arms under the following conditions:

- CR rates of 70% and 30% for patients receiving ACM and CM, respectively
- One-sided 2.5% significance level
- Randomization based on a 1:1 patient allocation ratio (ACM to CM)

The primary objective of Stage 2 is to compare CR rates between patients with relapsed or refractory AML with MCL-1 dependence of $\geq 30\%$ receiving 1 cycle of ACM treatment and those receiving 1 cycle of CM. Thus a patient who leaves the study prior to receiving one course of study treatment will be replaced by another eligible patient.

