5.2. Exploratory Study Arms

The sample size of 20 eligible patients in each of the four exploratory arms was selected because it allows estimation of the CR rate by means of a 90% confidence interval with maximum width of $\pm 18\%$.

6. Treatment Randomization

All patients participating in stage 1 of the primary study or an exploratory study arm will be assigned treatment with ACM. Randomization is not used in these parts of the study.

The remainder of this section refers only to patient participating in stage 2 of the primary study.

Stage 2 of the primary study follows a randomized, two-arm parallel design. The two treatment arms are ACM and CM. Dosages and infusion times are detailed in the study protocol.

Enrolled patients are randomized to receive ACM or CM in a 1:1 ratio and stratified by a three-category classification of response to first-line therapy:

- Refractory – defined as persistent disease or a CR duration less than 90 days
- Early Relapse – defined as a CR duration between 90 days and 1 year
- Late Relapse – defined as a CR duration greater than 1 year but less than 24 months

7. Statistical Methods

Statistical inference (hypothesis testing) to address the first and second objectives shown in section 4.2 will be addressed using data from stage 2 of the primary study only. Data from stage 1 of the primary study and the exploratory study arms will not be used for statistical inference.

Analyses will be performed using SAS statistical software. Default estimation methods in version 9.4 of SAS are always used unless an alternative is specified below. Data summaries will include the mean, standard deviation, median, minimum and maximum values for continuous data; the median, 25th and 75th percentiles, minimum and maximum values for time-to-event endpoints; and the number and percentage of patients in each category for categorical data. Pointwise 95% confidence intervals (CI) will also be estimated for the mean (continuous data), median (time-to-event endpoints) or percentage of patients (categorical data).

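### Protocol 11.4 combines non-randomised Stage 1 patients with Stage 2 ACM patients for secondary efficacy analyses, without limiting this to description and in conflict with the SAP

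*Protocol*

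**What the plan says.** Protocol 11.4, repeated in the Study Summary, restricts primary statistical comparisons to Stage 2 and then states that "data from Stage 1 patients will be combined with data from patients receiving ACM in Stage 2 for secondary efficacy analyses". It refers the reader to the SAP for details. SAP section 7 limits hypothesis testing for its first two objectives to Stage 2; the second of these (SAP 4.2) covers the secondary efficacy measures. It adds: "Data from stage 1 of the primary study and the exploratory study arms will not be used for statistical inference".

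Stage 1 is a single ACM arm. On its size, Protocol 4.1 says "Enrollment into Stage 1 will be limited to no more than 23 evaluable patients". Protocol 11.2.1 takes its go rule from a Simon design in which "the study would continue to Stage 2 only if 13 patients achieve remission out of a maximum of 23 eligible patients". Under Protocol 4.1 the rule counts CR, CRi or CRp, and Stage 1 closes once 13 are seen. That composite is Combined CR, which Protocol 11.4.2 places second in the testing hierarchy, directly after CR rate.

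On error control, Protocol 11.4 says: "The overall significance level for this study will be 2.5% using one-sided hypothesis tests".

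**The concern.** The secondary response endpoints are tested between arms with the same CMH test as the primary endpoint and sit in the alpha-controlled hierarchy. If Stage 1 patients join the ACM side of those tests, several things go wrong:

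- The comparison is no longer randomised.
- Pooled data exist only if Stage 1 met its go rule, so the Stage 1 remission rate is selected upward.
- Response criteria differ: IWG and 2010 ELN in Stage 1, 2017 ELN in Stage 2.
- The MCL-1 cutoff differs. Protocol 2.7 records the change from 40% to 30% at Amendment 11, and the protocol already speaks of Stage 1 response assessment in the past tense.
- OS and EFS run from randomisation, a date that Stage 1 patients do not have.

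The protocol's ITT definition (11.3) adds to the risk. It includes Stage 1 patients and is also the population named for efficacy hypothesis tests.

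**Working it through.** **Inputs.** One-sided 2.5% (Protocol 11.4). Stage 2: "The planned sample size of 56 patients (28 per treatment arm) in Stage 2 of this study provides 90% power", with "CR rates of 70% and 30% for patients receiving ACM and CM, respectively" (11.2.2). Stage 1: at most 23 patients, go at 13 remissions (4.1, 11.2.1). Simon rates 50% and 70% (11.2.1). The intermediate true rates of 55% and 60% are my assumptions.

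**The plan's own figures.**
- Stage 2 power with unpooled variance: 0.40/√(0.21/28 + 0.21/28) = 0.40/0.1225 = 3.266; 3.266 − 1.960 = 1.306; Φ(1.306) = 90.4%. The stated 90% is reproduced by this formula (the pooled-variance version gives 87.0%).
- Stage 1 90% interval half-width: 1.645 × √(0.25/23) = 17.1%, against the stated 17%.

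**Selection by the go rule.** Let X ~ Bin(23, p). With all 23 enrolled, the expected Stage 1 rate is E[X | X ≥ 13]/23, and the pooled ACM rate is (23 × that rate + 28p)/51. Examples:
- p = 0.70: (23 × 0.7117 + 19.6)/51 = 0.7053, or +0.5 points.
- p = 0.55: (23 × 0.6291 + 15.4)/51 = 0.5857, or +3.6 points.
- p = 0.50: (23 × 0.6138 + 14.0)/51 = 0.5513, or +5.1 points.

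If Stage 1 instead closes at the 13th remission, its size N (13 to 23) has probability proportional to C(N−1, 12) p^13 (1−p)^(N−13). The pooled rate is then the mean of (13 + 28p)/(N + 28).

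**Error of a pooled test.** Give ACM and CM the same true rate p, condition on the go rule being met, and reject when (a/n − b/28)/√[r(1−r)(1/n + 1/28)] ≥ 1.96. Here n is the pooled ACM size, a and b are the remission counts and r is the overall rate. The probabilities are summed exactly over all outcomes, without stratification. The CMH variance multiplies the term under the root by M/(M−1), with M the total number of patients. The error ranges span both variances and both closing rules.

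| True rate | P(go) | Stage 1 rate given go (23 enrolled / closes at 13th) | Pooled ACM bias, points | One-sided error |
|---|---|---|---|---|
| 70% | 94.5% | 71.2% / 72.7% | +0.5 / +0.8 | 2.9% |
| 60% | 71.3% | 65.0% / 66.7% | +2.2 / +2.5 | 3.5–3.6% |
| 55% | 52.8% | 62.9% / 64.7% | +3.6 / +3.9 | 4.1–4.4% |
| 50% | 33.9% | 61.4% / 63.2% | +5.1 / +5.5 | 5.0–5.6% |

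For comparison, the 28 versus 28 score test on Stage 2 alone has an exact one-sided error of 2.3% to 2.6% for common rates from 30% to 70%.

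**Which document governs.** The SAP names Amendment 7 as its protocol version and plans 106 Stage 2 patients, one interim analysis and an MCL-1 cutoff of 40%. The current protocol reflects Amendment 11, with 56 Stage 2 patients, no interim analysis and a cutoff of 30%. The hierarchies also differ. SAP section 4 says later amendments will be reviewed for their effect on the SAP, so its present rule could change.

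**The case against.** The strongest reply is that the pooled analysis was never meant as a test. Protocol 11.3 uses the word secondary for supportive, sensitivity analyses. Protocol 11.4.2 lets only the primary analysis of each endpoint decide significance. Stage 1 results are to be reported with descriptive statistics and confidence intervals, and the details are left to a SAP that excludes Stage 1 from inference. This stands in part: the text leaves open whether the hierarchy tests or only supportive analyses are meant. It does not remove the conflict, because the sentence has no such limit and the SAP follows a superseded amendment.

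The hierarchy also limits the harm. A secondary claim requires the Stage 2-only CR test to succeed first. If the arms are equal on every endpoint, false claims are held near 2.5% however later tests are pooled. Inflation needs a significant CR result together with a null secondary endpoint. The tabulated errors are also conditional on the go rule being met. Multiplied by that probability, the score-test error with 23 enrolled is 1.9% at 50%, 2.3% at 55% and 2.8% at 70%. Both points stand. The conditional error is still the relevant one, because a pooled analysis exists only after the rule is met.

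A reader might infer that pooling always favours ACM. The documents do not support that; only the go-rule component is shown to be upward. Stage 1 CR also required red cell transfusion independence, which Stage 2 drops (Study Summary). Protocol 2.7 reports lower response (52% against 62%) and 1-year survival (47% against 66%) in the group above 40% MCL-1 dependence than in the 30–39% group now eligible. Conversely, the 2017 criteria in Appendix E add absence of circulating blasts to the CR definition. The net sign is unknown.

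**Conclusion.** The point holds as an unresolved conflict between the protocol and the SAP over which patients may enter secondary efficacy analyses. The protocol's wording permits a non-randomised comparison. The documents do not establish that a biased test is definitely planned, or that the overall bias must favour ACM.

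The measurable part is selection by the go rule. It is small at the 70% design rate and reaches about 5 points, with roughly double the nominal error, at a true rate of 50%. These figures assume an unstratified test of remission on the go-rule composite (so they apply most directly to Combined CR), 28 patients per arm in Stage 2, and at most 23 in Stage 1 (Protocol 4.4.1 gives 25). They describe a single pooled test, not the rate of false claims after the hierarchy. For OS, EFS and transplant rate, the effect is indirect and cannot be computed from the documents.

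**What to change.** 1. In Protocol 11.4 and the Study Summary, replace the pooling sentence with: *All between-arm efficacy tests, primary and secondary, use randomised Stage 2 patients only; Stage 1 and Stage 2 ACM data may be shown together descriptively, labelled by stage and as non-randomised, and are not used in between-arm comparisons.*
2. Amend the ITT definition in Protocol 11.3 so that hypothesis tests use Stage 2 ITT patients only.
3. Carry the same rule into the SAP when it is updated to the current amendment.

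The cost is wording in two documents. Patients, sample size and conduct do not change, and the labelled descriptive display of all ACM data is kept.

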11.4.1 Demographics and Baseline Characteristics

Demographics and baseline characteristics will be summarized.

11.4.2 Efficacy Analyses

Response assessments in Stage 1 are defined by the International Working Group and 2010 ELN Criteria [20, 21]. The 2017 ELN criteria will be used to determine patient responses during Stage 2 [23] (*Appendix E*). The primary analysis for these response rates will be performed using data from all enrolled patients (intent-to-treat, ITT). In the ITT analysis, patients withdrawing from the study for any reason prior to a response assessment will be classified as a nonresponder. A secondary analysis of per protocol patients will also be performed.

Primary Efficacy Endpoint

- Complete Remission (CR) rate = Percentage of patients achieving CR

Secondary Efficacy Endpoints

- Combined CR Rate = Percentage of patients achieving a CR, CRi or CRp[†]
- Combined Response Rate = Percentage of patients achieving a CR, CRi, CRp[†], or PR
- Overall Survival (OS) = Time from randomization (Day 1) until death from any cause
- Event-free Survival (EFS) = Time from randomization (Day 1) until (a) treatment failure, (b) relapse after CR, or (c) death from any cause, whichever occurs first, censored at 2 years
- Rate of Stem Cell Transplantation = Percentage of patients proceeding directly to stem cell transplantation

[†]Note that CRp has been retained in definitions for Combined CR Rate and Combined Remission Rate because Stage-1 patients were assessed using the IWG criteria. CRp will not be used for assessing response in Stage-2 patients and, therefore, will not be included in the definitions of Combined CR Rate and Combined Remission Rate in Stage 2.

The CR rate in patients failing CM and crossing over to receive ACM will also be determined.

Secondary endpoints described for Stage 1/Stage 2 will also be assessed.

Additional exploratory analyses may be performed to assist the sponsor in planning future studies.

Without taking appropriate measures, testing multiple efficacy parameters inflates the overall significance level since the probability of making a type-1 error in at least one from a set of hypothesis tests is greater than the probability of making a type-1 error in any single test. The hierarchical closed test procedure will be used to maintain the overall 2.5% significance level.

The order of efficacy endpoints for the hierarchical closed test procedure is:

1. CR rate
2. Combined CR rate
3. Combined Response Rate
4. OS
5. EFS
6. Stem cell transplant rate

Each efficacy endpoint will be tested at a one-sided 2.5% significance level using the statistical procedures described above. CR rate, the primary efficacy endpoint, will be declared statistically significant if its test p-value ≤ 0.025 . A secondary efficacy endpoint will be declared statistically significant only if its test p-value ≤ 0.025 and all efficacy endpoints preceding it in the hierarchy are statistically significant. In other words, declaration of statistical significance for efficacy endpoints will advance in order down the hierarchy only until a p-value > 0.025 is found.

In addition, although there will be primary and supportive analytical methods for each endpoint in the hierarchy (supportive methods will be documented in the formal Statistical Analysis Plan), only the p-value from the primary analysis will be used for deciding statistical significance. Supportive (sensitivity) analyses are to demonstrate the robustness of primary results to slight modifications to how endpoints are defined and/or analyzed.

Declarations of statistical significance will not be advanced for endpoints not included in the hierarchy of the closed test procedure.

11.4.3 Pharmacodynamic Endpoint Analyses

Summary of baseline biomarker values will include within- and between-treatment-arm descriptive statistics. A logistic regression model will be fit to examine the relationship between baseline MCL-1 dependence and the independent binary variable achievement of CR during the study. The full model will include effects for baseline MCL-1 dependence, treatment arm, and the two-way interaction between baseline MCL-1 dependence and treatment arm. In addition, area under the curve (AUC) and 95% CI will be calculated (by treatment

arm) for the trapezoidal receiver operating characteristic curve. This value will quantify the ability of MCL-1 dependence to predict CR.

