4.5.3.4 Crossover (Stage 2)

- Patients randomized to CM with progressive disease or no response after one cycle of CM may cross over to receive ACM.
- Patients randomized to CM with a best response of PR after 2 cycles of CM may also cross over to receive ACM.

- Continued use of mitoxantrone is optional after completion of one cycle of ACM
- Mitoxantrone must be omitted from subsequent cycles if the patient's lifetime daunorubicin equivalent exceeds 460 mg/m² (see *Appendix G* for conversion table) or the left ventricular ejection fraction (LVEF) drops below 45%. Patients crossing over who meet the above criteria will receive only AC (alvocidib and cytarabine) for all cycles instead of ACM.
- Patients who cross over to ACM may receive up to a combined total (CM + ACM) of 4 cycles.

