- **Response-assessment population:** a subset of the safety population who have at least one response evaluation on study. When the response-assessment patient population is analyzed, patients are grouped according to actual treatment received. ACM is considered a patient's "treatment received" in the response assessment patient population if alvocidib is administered at any time prior to CR (or at any time during the study for patients never achieving CR). The response-assessment population is the primary population for assessing the correlation between MCL-1 dependency and response to ACM and is used for sensitivity (secondary, supportive) analyses of efficacy endpoints.

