7.9.1. Remission Rates

The primary efficacy endpoint is cycle-1 CR rate (i.e., the percentage of patients who achieve a CR after one cycle of treatment). Cycle 1 does not end until the patient starts cycle 2 or alternative AML therapy other than supportive measures (e.g., blood product transfusions). Therefore, a patient whose first response assessment in cycle 1 is a CRi or CRp* is considered to have achieved CR if neutrophils and platelets recover prior to initiation of cycle 2 or alternative AML therapy including bone marrow or stem cell transplant. Patients who, for any reason, do not supply bone marrow for response assessment are counted among those not achieving remission. Best response during the study (i.e., best response following one or more cycles of treatment) was not selected as the primary efficacy endpoint due to the anticipated confounding effects of patients who are randomized to CM but crossover after one or two cycles to receive treatment with ACM.

Three response assessments are planned for each postbaseline bone marrow sample:

1. The "central review" performed by a panel of independent, expert hematologists according to an approved charter under change control

* See footnote on page 6.

2. The “local review” of bone marrow and blood test results by the investigator at the study center where patient is enrolled
3. The “sponsor review” by employees and/or agents of Tolero Pharmaceuticals

It is beyond the scope of this SAP to restate or summarize the written charter detailing the methods and criteria the panel of hematologists use to grade response, but both central and local assessments are made according to criteria specified in the study protocol. The primary assessments of remission for comparing efficacy across treatment arms is the central review of bone marrow; however, in cases where the central hematologists are unable to rate response, the investigator’s response assessment will be used in place of the missing central assessment. Supportive efficacy analyses will be conducted using assessments from the local and sponsor reviews.

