7.10. Biomarker

The biomarker in this study is MCL-1 dependence measured by mitochondrial sensitivity to NOXA BH3 peptides. Relevant data supporting analyses of MCL-1 dependence will be listed by patient within treatment arm. Summary of baseline biomarker values will include within– and between–treatment-arm descriptive statistics appropriate for continuous variables (see section 7.7). An LR model will be fit to examine the relationship between baseline MCL-1 dependence and the independent binary variable cycle-1 CR for relapsed and refractory AML patients receiving ACM. In addition, area under the curve (AUC) will be calculated (by treatment arm) for the trapezoidal receiver operating characteristic (ROC) curve. This value will quantify the ability of MCL-1 dependence to predict cycle-1 CR.¹¹ Ninety-five percent CIs will be calculated by assuming estimated AUC follows a normal distribution.

$$\widehat{AUC} \pm z_{1-\alpha/2} SE_{AUC}$$

where the standard error SE_{AUC} is calculated by the jackknife method.¹² Data from relapsed/refractory patients receiving CM in cycle 1 and patients with newly diagnosed, high-risk AML will not be used in these analyses. Similar analyses will be conducted for (1) cycle-1 combined CR and (2) cycle-1 combined remission.

Quantifying the effect of MCL-1 dependence on response rates will not infer a safety and/or efficacy benefit (or detriment) of treatment with ACM over CM. Therefore, no statistical analyses of MCL-1 dependence across treatment arms are planned other than comparing baseline values to confirm randomization created homogeneous groups with respect to prestudy values.

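### Protocol 11.4.3 relates MCL-1 dependence to any CR during the study and fixes neither population nor grouping, so crossover to ACM distorts the by-arm analysis, in a way that depends on where crossover patients are counted

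*Protocol*

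**What the plan says.** **Outcome and model.** Protocol 11.4.3 fits a logistic model whose outcome is "the independent binary variable achievement of CR during the study". The terms are baseline MCL-1 dependence, treatment arm and "the two-way interaction between baseline MCL-1 dependence and treatment arm". It adds an AUC with 95% CI for each arm and states: "This value will quantify the ability of MCL-1 dependence to predict CR". The section names no analysis population.

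**Crossover.** Protocol 4.5.3.4 says: "Patients randomized to CM with progressive disease or no response after one cycle of CM may cross over to receive ACM". CM patients whose best response is PR after two cycles may also cross over, up to four cycles in total.

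**Protocol populations (11.3).** "The response-assessment population is the primary population for assessing the correlation between MCL-1 dependency and response to ACM". That population is grouped by treatment actually received. A patient counts as ACM if alvocidib was given before CR, or at any point if CR was never reached. There is no exception for crossover. The ITT population is grouped by randomized arm.

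**SAP.** Section 7.9.1 explains that best response during the study "was not selected as the primary efficacy endpoint due to the anticipated confounding effects of patients who are randomized to CM but crossover" to ACM. The same section specifies a logistic model of cycle-1 CR on MCL-1 dependence, arm and their interaction. Section 7.1 groups the response-available population, which it uses for biomarker analyses, by treatment received, but does not count ACM given after crossover. Section 7.10 models "the independent binary variable cycle-1 CR for relapsed and refractory AML patients receiving ACM" and asks for the AUC by treatment arm, yet leaves out patients who received CM in cycle 1. SAP Section 4 ties the SAP to Amendment 7; Protocol 2.7 describes Amendment 11.

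**The concern.** The CM curve and the interaction are what separate a predictive marker from a prognostic one: does MCL-1 dependence forecast CR only when alvocidib is given, or also without it? An outcome that runs past crossover blurs this, because a CM patient's CR during the study may be a CR on ACM. The SAP rejects an any-time response as the primary endpoint for this reason, while the protocol's biomarker section keeps one.

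At stake is a descriptive but central reading of a trial that is called biomarker-driven. Depending on grouping, either the CM arm picks up an MCL-1 relation that belongs to ACM, or the CM group is depleted of its failures.

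**Working it through.** **1. Planned rates.** Protocol 11.2.2 gives CR of 70% (ACM) and 30% (CM), 28 per arm, 90% power, one-sided 2.5%. With unpooled variance, n = (0.70×0.30 + 0.30×0.70)(1.960 + 1.282)² / 0.40² = 27.6, so 28 per arm, with power 90.4%. The plan's figure is reproduced. (A pooled-variance formula gives 31 per arm, and 87.0% power at 28.) The point does not rest on this figure; only the two rates are carried forward. The documents give no size, power or expected AUC for the MCL-1 model.

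**2. Assumptions (none is in the documents).** c is the share of CM cycle-1 failures who cross over, 0.50 or 0.75. q is their CR rate on ACM, 0.30 or 0.50. Crossover does not depend on MCL-1 dependence. MCL-1 dependence is uniform on 30-100%. It has no relation to CR on CM, and a slope of 0.50 logit per 10 points on ACM, also after crossover. Other CRs first reached after cycle 1 are ignored.

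**3. CR rates.**
- Crossover patients kept in CM: CM CR = 0.30 + 0.70·c·q.
- Crossover patients moved to ACM (Protocol 11.3): CM n = 28(1 − 0.70c); CM CR = 0.30/(1 − 0.70c); ACM CR = 0.70(1 + c·q)/(1 + 0.70c).

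| c | q | CM CR, kept in CM | CM n, moved | CM CR, moved | ACM CR, moved |
|---|---|---|---|---|---|
| 0.50 | 0.30 | 40.5% | 18.2 | 46.2% | 59.6% |
| 0.50 | 0.50 | 47.5% | 18.2 | 46.2% | 64.8% |
| 0.75 | 0.30 | 45.7% | 13.3 | 63.2% | 56.2% |
| 0.75 | 0.50 | 56.2% | 13.3 | 63.2% | 63.1% |

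With c = 0.75 and patients moved, a planned 70% against 30% shows as equal or reversed. With c = 1 the CM group would be 8.4 patients, all responders, and its AUC could not be estimated.

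**4. Interaction and AUC.** These are large-sample logistic slopes and AUCs. On cycle-1 CR by randomized arm the interaction is 0.50, with AUC 0.753 (ACM) and 0.500 (CM).

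| c | q | Interaction, kept | CM AUC, kept | Interaction, moved | CM AUC, moved |
|---|---|---|---|---|---|
| 0.50 | 0.30 | 0.366 | 0.577 | 0.418 | 0.500 |
| 0.50 | 0.50 | 0.344 | 0.589 | 0.477 | 0.500 |
| 0.75 | 0.30 | 0.303 | 0.613 | 0.407 | 0.500 |
| 0.75 | 0.50 | 0.259 | 0.636 | 0.474 | 0.500 |

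Loss when kept: 1 − 0.366/0.50 = 27% to 1 − 0.259/0.50 = 48%. Loss when moved: 1 − 0.477/0.50 = 5% to 1 − 0.407/0.50 = 19%. With a true slope of 0.25 the interaction is 0.120-0.176 (kept) and 0.211-0.241 (moved, a loss of 4-16%), and the CM AUC when kept is 0.54-0.58.

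**5. Changing the outcome only.** Suppose cycle-1 CR is used but Protocol 11.3's grouping stays. Every CM failure who crosses over then enters ACM as a non-responder. The interaction falls from 0.50 to 0.284 (c = 0.50) or 0.250 (c = 0.75), and the ACM AUC to 0.658 or 0.641. That is worse than the present wording under the same grouping (0.407-0.477 and 0.716-0.745).

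**6. Scale against noise.** With 8.4 CRs and 19.6 non-CRs expected in CM, the standard error of an AUC near 0.50 is about √[29/(12×8.4×19.6)] = 0.12. The CM AUC shifts of 0.08-0.14 are about one standard error.

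**The case against.** The strongest reply has four parts.

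- Protocol 11.3 names the population for the MCL-1 question and counts a patient whose CR follows crossover as ACM. A reader might infer from 11.4.3 that CM is always credited with ACM remissions and that MCL-1 dependence will therefore look merely prognostic. The documents do not support that in the 11.3 population, where the CM AUC does not move.
- A reader might also infer that no cycle-1 interaction model is planned. That is wrong: SAP 7.9.1 specifies one, and its Table 5 runs logistic regression in the ITT, per-protocol and response-available populations.
- Protocol Section 11 calls itself an overview and leaves detail to the SAP.
- The analysis is not a listed objective and sits outside the testing hierarchy. SAP 7.10 disclaims any inference about ACM over CM from it.

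All four stand as limits on size and importance. They do not remove the point. Protocol 11.4.3 speaks of treatment arm without naming a population, and the 11.3 sentence concerns response to ACM, not the CM curve or the interaction. The SAP's own rule for biomarker analyses does not count post-crossover ACM; joined to the protocol's outcome, it produces exactly the crediting of CM. Under 11.3 the distortion changes form: selection inflates the CM rate. The SAP models were also written to Amendment 7, and SAP 7.10 leaves the CM AUC undefined by asking for it by arm while excluding CM patients.

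**Conclusion.** The point holds as an unresolved mismatch of outcome, population and grouping, not as a single certain bias.

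- **Crossover patients kept in CM:** the CM AUC rises from 0.50 to about 0.58-0.64 and the interaction loses about 27-48%.
- **Crossover patients moved to ACM under Protocol 11.3:** the CM AUC stays at 0.50 and the interaction loses about 4-19%, but the CM CR rate rises from 30% to about 46-63% by selection and the arm term has no clear meaning.

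Neither grouping returns the planned 30% for CM. Cycle-1 CR grouped by cycle-1 treatment does, and it recovers the interaction in full. These sizes rest on assumed crossover shares, post-crossover CR rates, slopes and MCL-1 distribution, and on crossover being unrelated to MCL-1 dependence. They are large-sample shifts; with 28 per arm, sampling error will be of similar size. The primary CR comparison is not affected. The change should be made, but the trial's main conclusion does not depend on it.

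**What to change.** 1. In Protocol 11.4.3, make cycle-1 CR the outcome, assessed before any Cycle 2 or crossover dose. Name the population and group by randomized (cycle-1) treatment.
2. In Protocol 11.3, add the crossover exception that SAP 7.1 already has. This must accompany step 1, because changing the outcome alone makes the attenuation worse.
3. In SAP 7.10, resolve the conflict by computing the AUC on cycle-1 CR in both arms. Confirm the SAP 7.9.1 interaction model against the current protocol amendment.
4. Keep CR at any time as description only. Do not restrict it to patients who never crossed over: that selects on a post-randomization event and, at c = 0.50, lifts the CM rate from 30% to 46%.

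The cost is a few lines of text. Cycle-1 CR is already the primary endpoint, so no new data are needed. The downside is that CRs first reached in Cycles 2-4 drop out of the main biomarker analysis.
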